# 7.5. Replacement of Subjects

In the dose-escalation part of the study, subjects without a DLT who receive fewer than 10 doses through Cycle 2, Day 15 (C2D15) will be considered unevaluable for DLT assessment and will be replaced at the same dose level if the minimum number of evaluable subjects has not been reached for the cohort. However, the subject may remain in the study if the Investigator feels the risk/benefit ratio is acceptable. There will be no replacements of subjects other than subjects who are considered unevaluable for DLT assessment.

Subjects who discontinue for any reason, including disease progression, prior to the completion of the C2D15 visit in the dose-expansion part of the study (Part B) or in the combination therapy part of the study (Part C) will be replaced.

Data from subjects who are replaced will be included in the data analysis.

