#### Table 1:Study Design Overview

Portion of the Study	Cohort	ALKS 4230 Dose (µg/kg/day)
	1	0.1
	2	0.3
	3	1
	4	3
Dose Escalation (Part A) a	5	6
	6	8
	7	10
	8	12
	9	14
Dose Expansion (Part B)	Melanoma a	RP2D
(+ Extension Phase b )	RCC	RP2D
	ALKS 4230 1 µg/kg/day safety run-in	1
	ALKS 4230 3 µg/kg/day safety run-in	3
	C1:PD-1/L1 unapproved tumor types	3°
Combination Therapy	C2: PD-1/L1 approved tumor types (PD-1/L1 pretreated)	3°
(Part C) (+ Extension Phase b )	C3: PD-1/L1 approved tumor types (PD-1/L1 treatment naive)	3°
	C4: Rollover	3°
	C5: Melanoma	6 c
	C6: NSCLC	6 c
	C7: SCCHN	6 c

Abbreviations: DLT=dose-limiting toxicity, NSCLC=non-small-cell lung cancer, PD-1=programmed death receptor-1, PD-L1=programmed death ligand-1, RCC=renal cell carcinoma, RP2D=recommended Phase 2 dose, SCCHN=squamous cell carcinoma of the head and neck, TBD=to be determined.

a No more than 5 ocular melanoma subjects may be enrolled into this cohort.

b For subjects receiving clinical benefit from the treatment who are completing or have completed 1 year of treatment in Part B or Part C. Rollover subjects from Part A or Part B to Part C need to complete 1 year of treatment in Part C before entering the Extension Phase.

c A subject's ALKS 4230 dose may be reduced by one dose level as needed at the discretion of the Investigator.

If a subject without a DLT receives fewer than 10 doses before completing the C2D15 visit, the subject will be replaced, unless the minimum number of evaluable subjects for the cohort has been reached.

If dose escalation is not felt to be warranted, an intermediate dose between the current dose and the prior dose may be explored. Alternative dosing frequency (dosing less than 5 consecutive days in each treatment cycle) may also be explored depending on safety, PK, and pharmacodynamic observations during the dose-escalation portion of the study.

Dose-limiting toxicity will be defined by any of the following events possibly, probably, or definitely related to ALKS 4230 that are observed during the interval from Cycle 1, Day 1 through C2D15:

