- Grade 4 Neutrophil Count Decreased (neutropenia) that has not recovered to Grade 2 (≥1000 cells/µL) within 15 days of the start of the cycle or requires an urgent intervention (eg, use of hematopoietic colony-stimulating factors) or is associated with clinically significant infection. Dosing with ALKS 4230 in the current cycle will not be stopped due to neutropenia in the absence of urgent intervention or clinically significant infection.
- Febrile neutropenia (ANC <1000 cells/µL with temperature >38.3°C [100.9°F]) that persists for more than 48 hours or requires an urgent intervention (eg, use of hematopoietic colony-stimulating factors) or is associated with clinically significant infection
- CTCAE Grade 4 thrombocytopenia that does not recover to Grade ≤2 within 15 days of the start of the treatment cycle
- Thrombocytopenia equivalent to a platelet count <30,000 with clinically significant bleeding
- Any Grade 3 cardiac or central nervous system toxicity
- Liver transaminase elevation higher than 8 × ULN that does not recover to Grade ≤2 or baseline within 1 week or total bilirubin higher than 6 × ULN that does not recover to Grade ≤2 or baseline within 1 week
- Grade 4 hypoalbuminemia
- Fever  $>40^{\circ}C$  ( $>104^{\circ}F$ ) sustained for >24 hours
- Hypotension requiring the use of pressors (eg, phenylephrine or dopamine, administered for the purpose of increasing blood pressure) or prolonged hospitalization (>48 hours) for hypotension requiring medical intervention
- Grade 3 or higher electrolyte abnormalities that do not recover to Grade ≤1 within 48 hours following medical management
- Increase in amylase or lipase that meets one of the following criteria:
  - Asymptomatic Grade 4 elevation
  - Asymptomatic Grade 3 elevation that does not resolve within 14 days
  - >3× ULN with acute severe abdominal pain (other mild symptoms at Grade 3 will not be considered as DLTs)

- Grade 3 or higher nausea, vomiting, or diarrhea lasting longer than 48 hours despite maximum supportive care.
- Any other Grade 4 nonhematologic toxicity or any other Grade 3 non-hematologic toxicity that does not resolve to Grade ≤ 2 within 96 hours, except fatigue or anorexia. Fatigue and anorexia are not considered DLTs.
- Any other toxicity or AE not defined above that results in subject removal from the study or discontinuation of dosing by the Investigator. Dose delays during Cycle 2 or later are not considered DLTs.

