Any laboratory value that meets the DLT criteria as described above must be confirmed with a second laboratory result for DLT criteria to be met.

Subjects without a DLT who receive fewer than 10 doses through C2D15 will be replaced at the same dose level if the minimum number of evaluable subjects has not been reached for the cohort. However, the subject may remain in the study if the Investigator feels the risk/benefit ratio is acceptable.

Under certain circumstances an individual subject may be permitted to have his/her dose escalated (ie, intrapatient dose escalation). Refer to Section 9.6 for further details.

Subjects may remain on treatment until criteria for treatment discontinuation are met as described in Section 7.3. Subjects may remain on study until criteria for study discontinuation are met as described in Section 7.4. Note: all reasonable efforts should be made to encourage subjects to remain on study for follow-up evaluations even if they withdraw from treatment. For Part C, subjects who discontinue 1 drug (eg, due to unacceptable toxicity that cannot be managed by dose modification) must discontinue the entire study treatment.

In the Extension Phase, the treatment duration of monotherapy with ALKS 4230 may be extended until disease progression or until the subject meets any other criteria for treatment discontinuation (Section 7.3). Subjects in Part C are eligible to receive combination treatment for a maximum of 2 years of treatment in total (the initial phase plus the Extension Phase of Part C) for as long as the subject appears to be deriving clinical benefit (ie, objective response or SD) and has tolerated therapy well. Subjects may continue ALKS 4230 as a monotherapy beyond the maximum of 2 years of treatment — both in Part B by continuing treatment or in Part C by switching to monotherapy, at the joint discretion of the Investigator and Sponsor and if they do not meet any other criteria for discontinuation.

An interim review of the safety data to guide the selection of the RP2D is planned prior to the start of Part B of the study using data from subjects enrolled in Part A.

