- i Blood and urine samples for laboratory assessment will be collected. On dosing days, samples must be collected prior to dosing. For Cycle 1 Day 1, blood and urine assessment does not need to be repeated if performed at screening within 7 days of Cycle 1 Day 1. Samples for laboratory assessments may be drawn up to 72 hours prior to dosing on Day 1. See Section 8.3.10, Table 10 for assessments.
- j Serum tumor markers as appropriate. After Cycle 2, done only for even-numbered treatment cycles (eg, Cycles 4, 6, etc). See Section 8.3.10 for assessments.
- k A pregnancy test (urine or serum) must be given to all women of childbearing potential before each treatment cycle begins. Pregnancy test results must be confirmed as negative before the first dose of each cycle is administered for all cycles. Pregnancy testing may be performed up to 72 hours prior to dosing on Day 1.
-  Tumor imaging should include all appropriate radiographic procedures to document the full extent of the subject's known disease according to RECIST and iRECIST guidelines. Assessments are to be done at the end of Cycle 2 but before the next treatment cycle. For subsequent cycles, assessments are to be done at the end of each even-numbered treatment cycle (eg, Cycles 4, 6) but before the next treatment cycle. Tumor imaging should be done during the last week of the cycle.
- m Subjects will have tumor imaging scans every 9 weeks during the Follow-up Assessment Period (until the subject discontinues from the study or starts a new therapy).
- n ALKS 4230 will be given daily for Day 1 to 5 for each treatment cycle. For Cycles 1 and 2 for all dosing levels, all doses will be administered to subjects as inpatients at a medical facility with access to medical support measures and to the intensive care unit, if needed. Discharge is typically on Day 6 for Cycles 1 and 2. Dosing in subsequent cycles may be done as an outpatient. Anytime ALKS 4230 is administered, antipyretics should be administered prior (at least 15 minutes) to the infusion and should only be withheld at the discretion of the Investigator.

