#### 8.3.10. Laboratory Assessments

## 8.3.10.1. Hematology, Biochemistry, Microbiology, and Urinalysis

Blood and urine samples for laboratory assessments will be collected at the time points specified in Table 5, Table 6, Table 7, and Table 8. Specific hematology, biochemistry, and urinalysis assessments are listed in Table 10. Samples will be collected in accordance with the site's usual procedures and analyzed by the site's local laboratory for hematology, biochemistry, and urinalysis.

Fasting is not required prior to sample collection for laboratory assessments.

In the event that any microbiology specimens are obtained for culture, results should be recorded in the eCRF.

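### Two Part A DLT criteria for asymptomatic amylase or lipase elevation depend on tests that none of the 8 scheduled biochemistry draws after first dose through C2D15 includes

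*Protocol*

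**What the plan says.** **DLT definition.** Protocol 8.1 counts related events "that are observed during the interval from Cycle 1, Day 1 through C2D15". One item is an "Increase in amylase or lipase that meets one of the following criteria", followed by three criteria:

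- an asymptomatic Grade 4 value;
- an "Asymptomatic Grade 3 elevation that does not resolve within 14 days";
- a value above 3 times ULN accompanied by sudden severe abdominal pain.

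A laboratory DLT "must be confirmed with a second laboratory result for DLT criteria to be met". SAP 9.2 carries the same three criteria and the same confirmation rule.

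**What is measured.** Protocol 8.3.10.1 states: "Specific hematology, biochemistry, and urinalysis assessments are listed in Table 10". Table 10 lists general chemistry, liver and renal tests, TSH and tumour markers, but neither amylase nor lipase. The panel in SAP 9.4 also lists neither. Table 5, the Part A schedule, has no separate row for them, and its footnote i refers back to Table 10. The same footnote says: "On dosing days, samples must be collected prior to dosing", and "For Cycle 1 Day 1, blood and urine assessment does not need to be repeated if performed at screening within 7 days".

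**Who is evaluable.** Protocol 7.5 says that "subjects without a DLT who receive fewer than 10 doses through Cycle 2, Day 15 (C2D15) will be considered unevaluable for DLT assessment". No condition requires that the laboratory values behind the DLT criteria were obtained.

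**How it is reported.** DLT incidence is a primary Part A endpoint (Protocol 6.4). SAP 9.2 tabulates DLTs by system organ class, preferred term and cohort, with a listing.

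**The concern.** The other DLT criteria tied to a named laboratory value have their analyte in Table 10: neutrophils, platelets, transaminases, total bilirubin, albumin and electrolytes. For those, a subject who followed the schedule and shows no event was looked at and found clear. Amylase and lipase are the exception. The criterion exists and a confirming second result is required, but the schedule supplies no first result.

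A site that follows the visible plan exactly, and orders nothing beyond it, cannot find an asymptomatic Grade 4 value or a persistent asymptomatic Grade 3 value. Its subject still enters the DLT denominator as event-free.

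The reporting rules do not reveal this. Under SAP 13.2.5.2, unordered categories with no subject are left out of tables. Under SAP 6.2.7, unscheduled values are generally kept out of the laboratory summaries and appear in listings. The DLT table therefore gives no sign of whether a missing amylase or lipase line means no event or no test.

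**Working it through.** The plan states no figure of its own on this point, so the check sets the schedule against the panel.

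**Step 1. Draws in the DLT window.** Inputs: the Part A biochemistry row of Protocol Table 5, and a Cycle 1 length of 14 days. The nominal study day is the cycle day in Cycle 1, and 14 plus the cycle day in Cycle 2. The window closes at C2D15, which is day 14 + 15 = 29.

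| Draw | Study day | Before that day's infusion? | Amylase or lipase in panel | Day + 14 | Within day 29? |
|---|---|---|---|---|---|
| C1D3 | 3 | yes | no | 17 | yes |
| C1D5 | 5 | yes | no | 19 | yes |
| C1D8 | 8 | no dose that day | no | 22 | yes |
| C2D1 | 15 | yes | no | 29 | yes |
| C2D3 | 17 | yes | no | 31 | no |
| C2D5 | 19 | yes | no | 33 | no |
| C2D8 | 22 | no dose that day | no | 36 | no |
| C2D15 | 29 | no dose that day | no | 43 | no |

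There are 8 draws after the first dose, 5 of them taken before that day's infusion. The C1D1 draw precedes all dosing and may be replaced by a recent screening sample, so it could serve only as baseline.

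**Step 2. Coverage.** Draws that include either analyte: 0 of 8. Neither is in the screening or C1D1 panel, so there is no scheduled baseline value either.

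**Step 3. Criteria affected.** 2 of the 3. The criterion that needs severe abdominal pain is not affected in the same way, because the symptom would prompt a test.

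**Step 4. Evaluability.** Two cycles of 5 daily doses give 2 × 5 = 10 doses. A subject with all 10, no other DLT and no unscheduled amylase or lipase test meets the Protocol 7.5 rule and counts as DLT-free.

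**Step 5. What the existing visits could support.** If the analytes were added, four pairs of draws lie exactly 14 nominal days apart: 3/17, 5/19, 8/22 and 15/29. Persistence at 14 days could be shown inside the window only for an elevation first seen by C2D1, that is, at 4 of the 8 draws. For the other four, the fourteenth day falls after day 29. A Grade 4 value needs no waiting period, only the confirming result.

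**Step 6. Added work.** 2 analytes × (1 baseline + 8 later draws) = 18 results per subject.

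The number of missed DLTs cannot be derived, because the documents give no rate for these elevations and no count of unscheduled tests.

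**The case against.** The strongest reply is that a DLT list classifies events and does not by itself set a surveillance schedule. Only observed events count. Without this item, the catch-all for other non-haematologic toxicity would make a Grade 3 value unresolved after 96 hours a DLT. The amylase/lipase item lengthens that to 14 days for asymptomatic Grade 3 values and excludes mild symptoms at Grade 3, so it can be read as a deliberate relaxation for values found incidentally. That reading is fair for Grade 3. It still leaves an asymptomatic Grade 4 value as a DLT, and observing one requires a test.

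There are also routes by which such an event could be recorded. Protocol 13.1 makes clinically significant laboratory values adverse events, and is not limited to the Table 10 analytes. Escalation goes through Safety Review Committee review of the cohort's safety data. Sections 9.6.2, 9.6.4 and 9.7 are blank or redacted, 9.8 largely so, and the list of tables runs from Table 11 to Table 14, so guidance on ad hoc testing may exist out of view. All of this stands, and it limits the point to the scheduled panel. These routes help only where someone orders an unscheduled test.

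A reader might go further and infer three things that the documents do not support:

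- **That any asymptomatic elevation is a DLT.** The grade, persistence, relatedness and confirmation conditions all apply.
- **That Part A subjects were never tested.** Local laboratories may have run these tests, and the documents do not say.
- **That dose escalation went too far or that the RP2D is too high.** Any such calculation needs an event rate, and none is given. The nonclinical target organs were lung, liver and spleen (Protocol 5.3), which gives no reason to expect a pancreatic signal.

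**Conclusion.** The point holds as a minor one. Protocol 8.1 and SAP 9.2 define two asymptomatic amylase/lipase DLTs that 0 of the 8 scheduled biochemistry draws after first dose through C2D15 can detect, and a fully dosed subject with no other DLT and no unscheduled test is counted as DLT-free.

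The direction is fixed: missing tests can only lower the observed DLT count on a primary Part A endpoint. The size is zero or more and may be near zero. No effect on escalation is shown, nor on the RP2D of 6 µg/kg recorded in SAP 3.4. With that dose set, and SAP 6.1 tabulating Part A only to 10 µg/kg, what remains is mainly how the Part A DLT table is read.

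The conclusion rests on the visible text: Table 10, the SAP 9.4 panel, Table 5 and the evaluability rule. Redacted text that called for ad hoc testing would reduce the practical consequence, but would not by itself put the analytes in the scheduled panel.

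**What to change.** **Subjects already treated (SAP 9.2, Part A DLT table).** Add one row per dose cohort giving the number and percentage of subjects with at least one recorded amylase or lipase result after first dose through C2D15. Add a footnote stating that these analytes were not in the scheduled panel, so the two asymptomatic criteria were assessed only where unscheduled results were recorded. The cost is one row and one footnote. The row counts recorded results, so it cannot separate a subject who was not tested from one whose result was not entered; if no results were entered, it reads 0.

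**Any Part A subject or dose level still to be enrolled (Protocol Table 10).** Add amylase and lipase to the baseline draw (screening or C1D1 predose) and to the 8 existing draws through C2D15. State that 14-day persistence can be shown within the window only for elevations first seen by C2D1. DLT thresholds and escalation rules stay as they are. The cost is 18 local-laboratory results per subject with no extra visit, plus the repeat test already required to confirm a value that meets a criterion. The downside is that incidental confirmed elevations will then count as DLTs, as the criterion intends.

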#### Table 2: Simon's Two-stage Design Enrollment for Subjects in Part B

Abbreviations: CR=complete response, PR=partial response, RCC=renal cell carcinoma.

a No more than 5 ocular melanoma subjects may be enrolled into this cohort.

The RP2D will be equal to or less than the MTD and its associated dosing schedule and will be selected based on the safety, PK, pharmacodynamics, and preliminary antitumor activity data observed during dose escalation.

An independent data monitoring committee (IDMC) will review accumulating safety and efficacy data at regular intervals and monitor overall study conduct beginning in the second stage (N2) of Part B cohorts and Part C C5, C6, and C7 cohorts (see Section 14.6 for details).

In the third part of the study (Part C), subjects will receive ALKS 4230 in combination with pembrolizumab. Part C will run independently of and concurrently with monotherapy Part A and Part B.

A 3- to 6-subject run-in phase will be utilized to assess the safety of ALKS 4230 in combination with pembrolizumab. During the safety run-in phase, subjects may be enrolled with any tumor type as described in the nonrollover cohorts. Rollover subjects (Cohort 4) are not eligible to participate in the safety run-in phase of Part C.

During the safety run-in phase, the first 3 subjects will receive ALKS 4230 at the dose level of 1  $\mu$ g/kg/day. The first subject enrolled at the 1  $\mu$ g/kg/day dose level will be monitored as a sentinel subject. This sentinel subject will be observed for safety for a period of 7 days (the sentinel period) from first dose of ALKS 4230. If the sentinel subject tolerates treatment adequately during this period, then up to 2 additional subjects may be enrolled into the 1  $\mu$ g/kg/day dose level. If all 3 subjects tolerate therapy adequately through their first 21-day cycle as assessed by the SRC, then the study will progress to the 3  $\mu$ g/kg/day dose level. At the discretion of the SRC, an additional 3 subjects may be enrolled at the 1  $\mu$ g/kg/day dose level to further assess safety prior to opening enrollment at the 3  $\mu$ g/kg/day dose level.

Once the safety run-in phase at the 1  $\mu$ g/kg/day dose level is complete and the SRC has agreed to proceed to the 3  $\mu$ g/kg/day dose level, the first subject will be enrolled at the 3  $\mu$ g/kg/day dose level and will be observed for 7 days as a sentinel subject. If this subject tolerates treatment adequately for 7 days, then up to 2 additional subjects may be enrolled in the following week. If the second and third subjects tolerate the 3  $\mu$ g/kg/day dose level adequately for 7 days, then 3 additional subjects can be enrolled beginning the following week.

If the first 6 subjects tolerate therapy adequately for their first 21-day cycle as assessed by the SRC, then enrollment into expansion Cohorts C1, C2, C3, and C4 will be open without restriction in the rate of enrollment at the dose determined by the SRC.

Up to 20 subjects will be enrolled into each of Cohorts C1, C2, C3 based on their tumor type and prior treatment with PD-1/PD-L1 pathway inhibitors as described in the inclusion criteria. Subjects with RCC or melanoma will not be eligible for enrollment in Cohorts C1, C2, or C3. Subjects on ALKS 4230 monotherapy in Part A or Part B who have experienced disease progression after a minimum of 2 cycles or SD after a minimum of 4 cycles and who are expected to tolerate treatment with combination therapy are eligible for treatment in Part C, Cohort C4. Subjects who have PR or CR on monotherapy are ineligible to rollover unless subsequently demonstrating progressive disease.

Subjects will receive 200 mg of pembrolizumab every 3 weeks in combination with ALKS 4230 by IV administration daily for 5 days, followed by a period off treatment of 16 days, resulting in a cycle length of 21 days (3 weeks) for each cycle.

Once a RP2D is determined for monotherapy, enrollment into Cohorts C5, C6, and C7 will open. Should monotherapy doses above 6  $\mu$ g/kg/day ALKS 4230 be shown to be tolerated, then the dose of ALKS 4230 in the combination arms may be increased. In Cohorts C5, C6, and C7, up to 53 subjects with melanoma, up to 42 subjects with NSCLC, and up to 36 subjects with squamous cell carcinoma of the head and neck may be enrolled to receive ALKS 4230 in combination with pembrolizumab at the RP2D. Enrollment to these cohorts will follow a PR (unconfirmed) Simon's two-stage enrollment as outlined below. Response assessments will be based on RECIST and iRECIST guidelines.

	Undesirable Rate	Desirable Rate	N1	Enroll More if	N2	Total
C5: Melanoma	40%	55%	27	≥12 PR/CR	26	53
C6: NSCLC	13%	27%	18	≥3 PR/CR	24	42
C7: SCCHN	15%	30%	17	≥3 PR/CR	19	36

 Table 3:
 Simon's Two-stage Design Enrollment for Subjects in Part C

Abbreviations: CR=complete response, NSCLC=non-small-cell lung cancer, PR=partial response, SCCHN=squamous cell carcinoma of the head and neck.

If the monotherapy RP2D is determined by the SRC to be 6  $\mu$ g/kg/day or above, intrapatient dose escalation may be considered for subjects in Cohorts C1, C2, C3, and C4 who had been assigned to the 1  $\mu$ g/kg/day or 3  $\mu$ g/kg/day dose levels and had adequately tolerated the combination therapy.

Table 4:Planned Number of Subjects for Part C

Expansion Cohort: Tumor (Setting)	Number of Subjects
C1: PD-1/L1 unapproved tumor types a	Up to 20
C2: PD-1/L1 approved tumor types (PD-1/L1 treatment pretreated) a	Up to 20
C3: PD-1/L1 approved tumor types (PD-1/L1 treatment naive) a	Up to 20
C4: Monotherapy Rollover	Not applicable
C5: Melanoma	Up to 53

Table 4:Planned Number of Subjects for Part C (	Continued)
---	------------

Expansion Cohort: Tumor (Setting)	Number of Subjects
C6: NSCLC	Up to 42
C7: SCCHN	Up to 36

Abbreviations: C=Cohort, NSCLC=non-small-cell lung cancer, PD-1/L1=programmed death

receptor-1/programmed death ligand-1, RCC=renal cell carcinoma, SCCHN=squamous cell carcinoma of the head and neck.

a Subjects with RCC or melanoma are not eligible for enrollment in Cohorts C1, C2, and C3.

